12.1.4 Overview of Adverse Events

For the APTS and APTS-OL, respectively, an overview of the numbers and percentages of participants with TEAEs, TEAEs related to IMP, serious adverse events (SAE)s, TEAE intensity (Mild, Moderate, Severe), TEAEs leading to infusion interruption, TEAEs leading to withdrawal from treatment, and TEAEs in participants who died will be provided. For the APTS-FU, an overview of the numbers of participants with TEAEs, TEAEs related to IMP, SAEs, and TEAEs in participants who died will be provided. For TEAEs, TEAEs related to IMP, and SAEs, the total number of events will be provided.

A listing of all adverse events occurring before entering the Open-label Period, including a flag for TEAEs will be provided based on APRS. For participants in the APTS-FU set, adverse events reported after withdrawal in the Placebo-controlled Period but before Week 12, will be included in this list.

A listing of all adverse events starting at or after entering the Open-label Period, including a flag for TEAEs will be provided based on the APTS-OL.

For participants who do not enter the Open-label Period, for example study withdrawals during the Placebo-controlled Period, a separate listing of TEAEs with start date after Week 12 will be provided based on the APTS-FU.

12.1.5 Treatment-emergent Adverse Events

The following summaries will be provided by treatment group for the Placebo-controlled Period and by treatment sequence for the Open-label Period:

- TEAEs by SOC and preferred term
- TEAEs with an incidence $\geq 2\%$ in any treatment group by preferred term
- causally related TEAEs by SOC and preferred term
- TEAEs by intensity (*mild/moderate/severe*), SOC, and preferred term
- causally related TEAEs by intensity, SOC, and preferred term
- TEAEs occurring on the day of dosing after infusion start by SOC and preferred term (this includes day of Visit 2 infusion for the Placebo-controlled Period and day of Visit 5 infusion for the Open-label Period)

The summaries will be provided for the APTS for the Placebo-controlled Period and for APTS-OL for the Open-label Period.

12.1.6 Serious Adverse Events

Treatment-emergent SAEs will be summarized by treatment group for the Placebo-controlled Period based on APTS and by treatment sequence for the Open-label Period based on APTS-OL by:

- SOC and preferred term

All SAEs occurring before entering the Open-label Period will be listed for the APRS.

All SAEs occurring at or after entering the Open-label Period will be listed for the APTS-OL.

12.1.7 Adverse Events Leading to Withdrawal from Treatment

TEAEs leading to withdrawal will be summarized for by treatment group the Placebo-controlled Period based on APTS and by treatment sequence for the Open-label Period based on APTS-OL by:

- SOC and preferred term

All AEs leading to withdrawal before entering the Open-label Period will be listed for the APRS.

All AEs leading to withdrawal occurring at or after entering the Open-label Period will be listed for the APTS-OL.

12.1.8 Adverse Events Leading to Trial Drug Infusion Interruption

All AEs leading to trial drug infusion interruption before entering the Open-label Period will be listed for the APRS.

All AEs leading to trial drug infusion interruption occurring at or after entering the Open-label Period will be listed for the APTS-OL.

TEAEs leading to trial drug infusion interruption will be summarized for the Placebo-controlled Period based on APTS and for the Open-label Period based on APTS-OL by:

- SOC and preferred term

12.1.9 Deaths

All the adverse events in participants who died before entering the Open-label Period will be listed for the APRS.

All the adverse events in participants who died after entering the Open-label Period will be listed for the APTS-OL.

12.1.10 Adverse Events of Special Interest

Treatment-emergent adverse events of special interest (AESI) will consist of the preferred terms defined by the SMQs/HLTs/HLGTs listed in Table 15 .

The following summaries of treatment-emergent AESIs will be provided by treatment group for the Placebo-controlled Period based on the APTS and by treatment sequence for the Open-label Period based on the APTS-OL:

- AESIs by SOC and preferred term
- AESIs by SOC and preferred term, separately for each individual event category

All AESIs occurring before entering the Open-label Period will be listed for the APRS.

All AESIs occurring at or after entering the Open-label Period will be listed for the APTS-OL.

The listings will be repeated for all AEs belonging to the Hypersensitivity and Anaphylactic Reactions event category only, see Table 15.

12.2 General Methodology for Other Safety Data

Unless otherwise specified, tables, graphs, and listings will be based on the APTS for the Placebo-controlled Period and APTS-OL for the Open-label Period.

All tables and graphs will be presented by treatment group for the Placebo-controlled Period and by treatment sequence group for the Open-label Period.

The denominators for the summaries of a given variable will be based on the number of participants with non-missing values at a given visit or during the assessment period.

Descriptive statistics for the safety variables, both absolute values and changes from baseline, will be presented by visit, separately for each period.

12.3 Vital Sign Measurements

Vital signs including blood pressure, pulse, respiratory rate, and temperate will be summarized based on APTS in Placebo-controlled Period and APTS-OL in Open-label Period by position, visit and treatment group.

Summary of participants with potentially clinically significant vital sign results will also be summarized using the PCS criteria in Appendix 17.2. The number and percentage of participants with at least one potentially clinically significant (PCS) value at any post-baseline assessment time point will be summarized by vital signs, separately for each period. All available assessments in each period will be included in the evaluation of PCS values.

For participants with post-baseline PCS values in the Placebo-controlled Period, listings will be provided including all the values for those participants for the variable prior to entering the

Open-label Period, with flagging of PCS values and out-of-reference-range values. For participants with PCS values occurring after start of Visit 5 IMP infusion, similar listings will be provided including all the values for those participants for the variable. For participants in the APTS-FU set, i.e. for the participants who do not enter the Open-label Period, for example study withdrawals during the Placebo-controlled Period, with PCS values occurring after Week 12, similar listings will be provided including all the values for those participants for the variable.

12.4 Other Safety Endpoints

12.4.1 Screening Assessments

Clinical laboratory, ECG, reproductive system, physical and neurological examinations are performed at screening. Any abnormal finding or out-of-range value considered clinically significant by the investigator will be recorded as an adverse event on an *Adverse Event Form*.

The Columbia-Suicide Severity Rating Scale (C-SSRS)³ is a semi-structured interview developed to systematically assess suicidal ideation and behaviour of participants participating in a clinical trial. The C-SSRS has 5 questions addressing suicidal ideation, 5 sub-questions assessing the intensity of ideation, and 4 questions addressing suicidal behaviour. For this trial, the following versions of the scale are used: the “Baseline/Screening” version (lifetime and 1 year assessment).

Table 5 C-SSRS Scores

C-SSRS Score	Related to:
1 Wish to be dead	Suicidal ideation
2 Non-specific active suicidal thoughts	
3 Active suicidal ideation with any methods (not plan) without intent to act	
4 Active suicidal ideation with some intent to act, without specific plan	
5 Active suicidal ideation with specific plan and intent	
6 Preparatory acts or behaviour	Suicidal behaviour
7 Aborted attempt	
8 Interrupted attempt	
9 Non-fatal suicide attempt	
10 Completed suicide (only applicable for the post-baseline assessments)	

13 Interim Analysis

No interim analysis is planned.

14 Sample Size Considerations

The sample size calculation assumes that the treatment effect of eptinezumab 100 mg compared to placebo in change from baseline in MMDs (Weeks 1 to 4) will be -1.5 MMDs. The difference between eptinezumab 100 mg and placebo was -2.0 in Study 011, a trial that did not include education on MOH, after 4 weeks and -3.1 in the subgroup of participants with CM and MOH. The difference between withdrawal from treatment with and without preventive treatment was -1.7 and -1.4 days after 2 and 4 months. The SD is assumed to be 6.2, based on the averaged SD

across treatment groups in the MOH subgroup of Study 011 on the change from baseline in MMDs (Weeks 1 to 4).

Based on the assumed effect size and SD, using a two-sided test on the 5% significance level, 270 participants per treatment group will provide 80% power for showing an effect on the primary endpoint. Assuming that 5% of participants will not contribute data to the analysis. 285 participants randomized per treatment group, or 570 participants randomized in total will be needed.

A sample size re-assessment will be conducted on blinded data when approximately 70% of the participants have been randomized. The SD is estimated in the same model as for the primary endpoint, except that all terms including treatment (main effect of treatment group and interaction between treatment group and month) are excluded. Based on this estimate, the sample size may be increased.

15 Details on Data Handling

15.1 eDiary

15.1.1 Monthly Migraine Days /Monthly Headache Days

The following describes the derivation of MMDs. The derivation of MHDs follows the same principles. Definitions of a migraine day and a headache day are described in Section 3.6.

Pooling of symptoms

To assess whether a headache is a migraine headache, daily reported symptoms will be pooled to assess the migraine criteria described in Section 3.6. The worst reported symptom will be used, for example, if different levels of worst pain have been reported on different days of the same headache, the worst of these levels will be used to assess the migraine criteria.

Regarding successful medication use for the criterion “a headache that is successfully treated with a triptan, ergotamine, or other migraine-specific acute medication”: a medication can only be considered successful if the question *“Did at least one of the medications you took today successfully treat your headache?”* is answered positively on the same day as the medication intake date.

4-Week Intervals

For Baseline and each 4-week period post-baseline in the trial, the number of MMDs will be derived as the number of migraine days within each 28-day interval using the imputation rules described below. The 4-week periods post-baseline that are considered are the following: Weeks 1-4, Weeks 5-8, Weeks 9-12, Weeks 13-16, Weeks 17-20 and Weeks 21-24.

In general, for 4-week periods where the number of reported eDiary days are at least 14 days out of the 28 days, prorating will be used to calculate the MMDs, and for 4-week periods where the number of reported eDiary days are less than 14 days out of the 28 days, the MMDs will be set to missing. Once prorating has been applied, a non-missing 4-week MMD value is considered a valid assessment.

Prorating

Intended to be used for 4-week periods where the eDiary is completed on at least 14 out of the 28 days, the prorating procedure consists of imputing days with missing information with the observed mean number of migraine days in the period as follows:

$$28^*(\text{Reported Migraine Days}/\text{Reported eDiary Days})$$

This imputation rule will also be used for the Baseline value regardless of the number of reported eDiary days in the screening period.

When the number of MMDs have been calculated for a given 4-week period, the result will be rounded to two decimals.

15.1.2 Migraine/Headache Responder Rates

The following describes the derivation for migraine responder rates. The derivation for headache responder rates is similar.

The following responder rates will be derived: 50% and 75%. A responder is a participant, who achieves a $\geq 50\%$ reduction or $\geq 75\%$ reduction, respectively, compared to the baseline number of MMDs. The derivation of these responder endpoints will be based on the number of MMDs resulting from the imputations described in the Section 15.1.1.

For each 4-week period post-baseline in the trial, the responder status of a participant will be derived based on the percentage change from baseline in MMDs. If the MMDs value is missing for the month in question, the response status will also be missing.

For Weeks 1-4, the 50% and 75% responder status will be derived as follows, using 50% response as an example:

$$50\% \text{ Responder Status(Weeks 1 - 4)} = \begin{cases} 1, & \text{if } \frac{(\Delta_{M1})}{\text{Baseline}} \leq -0.5 \\ 0, & \text{if } \frac{(\Delta_{M1})}{\text{Baseline}} > -0.5, \end{cases}$$

For Weeks 1-12, the 50% and 75% responder status will be derived as follows, using 50% response as an example:

$$50\% \text{ Responder Status(Weeks 1 - 12)} = \begin{cases} 1, & \text{if } \frac{\text{ave}(\Delta_{M1}, \Delta_{M2}, \Delta_{M3})}{\text{Baseline}} \leq -0.5 \\ 0, & \text{if } \frac{\text{ave}(\Delta_{M1}, \Delta_{M2}, \Delta_{M3})}{\text{Baseline}} > -0.5, \end{cases}$$

where Δ_{Mi} is the change from baseline value for month i . For 12-week intervals, if any of the months included in the calculation have a missing value of MMDs after prorating, the responder status will be derived based on the available values.

15.1.3 Percentage of Participants with Migraines on the Day After Dosing (Day 1)

The percentage of participants with a migraine on the day after dosing will be derived based on whether the participant filled out the eDiary on Day 1 or not. If the participant filled out the eDiary on Day 1, the participant will have a rate of either 0 or 100 on Day 1 that is 0 if the

participant experienced no migraine on Day 1 and 100 if the participant did experience a migraine on Day 1.

If the participant did not fill out the eDiary on Day 1, the rate for the participant will be imputed as:

$$100 * (\text{Number of MMDs Weeks 1-4}/28),$$

where the number of MMDs for Weeks 1-4 is derived as described in Section 15.1.1. Note that if the number of MMDs for Weeks 1-4 is missing for the participant and the participant did not fill out the eDiary on Day 1, the Day 1 rate will be missing.

15.1.4 Migraines/Headaches with Severe Pain Intensity and Migraine Attacks/Headache Episodes

The percentage of migraines/headaches with severe pain intensity is derived based on the derived number of monthly migraine attacks and headache episodes.

Migraine attack and headache episodes are defined in the Section 3.8. Headache severity is collected on a 3-point scale, Mild, Moderate and Severe. Migraines and headaches with severe pain intensity on at least one day are defined as migraine attacks/headache episodes with a reported severity of “Severe”.

The following describes the derivation of number of monthly migraine attacks. The derivation of monthly headache episodes follows the same principles.

The derivation of the number of monthly migraine attacks will follow the imputation rules described in Section 15.1.1 for MMDs, replacing *Reported Migraine Days* with *Reported Migraine Attacks* everywhere. As an example, the number of monthly migraine attacks for a participant with 14 days or more of eDiary reporting in a 4-week period will be derived as:

$$28 * (\text{Reported Migraine Attacks}/\text{Reported eDiary Days})$$

The number of monthly migraines with severe pain intensity is derived in the same way using only migraine attacks with a reported severity of “Severe”.

The percentage of migraines and headaches with severe pain intensity is then calculated as the percentage of migraine attacks/headache episodes with severe pain intensity out of the number of migraine attacks/headache episodes. Participants with no migraine attacks/headache episodes are included with a rate of 0.

15.1.5 Monthly Days with Acute Migraine Medication Usage and MMDs with Acute Migraine Medication Usage

In the aura without headache and headache diaries, as well as the evening diary, participants are asked each day to fill out whether they used any of the following medications during that day: ergotamine, triptan, non-opioid analgesic, barbiturates, opioid, or combination analgesic. A day where the participant answers that they took any of those in the diary is considered a day with use of acute migraine medication.

The number of days with acute migraine medication usage is then derived for each 4-week period using the imputations described in Section 15.1.1 and replacing *Reported Migraine Days* with *Reported Acute Migraine Medication Days* everywhere as well as replacing *Reported eDiary Days* with *Reported Medication Days*, where a “*Reported Medication Day*” is defined as

a Reported eDiary Day where at least one of the following pieces of information are available:

- A response in the Headache eDiary question “Did you take any medications to treat this headache today?”
- A response in the Evening eDiary question “Did you take any medication to prevent a headache today?”
- A response in the Aura without Headache eDiary question “Did you take any headache medication related to this aura today?”

A missing Medication Day is defined as a day that is not a Reported Medication Day.

If a reported acute migraine medication span across two 4-week periods, then it will be counted in both periods according to the medication start date/preceding period end date and subsequent period start date/medication end date.

The number of days with each available medication type taken will be derived in a similar manner as above.

Additionally, the MMDs with acute migraine medication usage will be derived. The number of MMDs with acute migraine medication is derived in a similar manner as above, except that only days that qualify as a migraine day will be considered.

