3.7 Definition of a Reported eDiary Day and a Missing eDiary Day

A reported eDiary day is a day where at least one of the following pieces of information are available:

- A headache event is reported to take place and the participant has recorded the daily symptoms for at least one of the days spanned by this headache
- The headache eDiary has been completed, and it has been confirmed that no headaches happened on this day
- Aura without headache diary is reported with a taken medication

A missing eDiary day is defined as a day that is not a reported eDiary day.

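### A headache day with the treatment question blank can count as a day without acute medication, because an answer to the evening prevention question alone makes it a reported day

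*SAP*

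**What the plan says.** SAP 15.1.5 derives monthly acute medication days by the prorating formula of SAP 15.1.1, with medication days in the numerator and Reported Medication Days in the denominator.

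- **Denominator.** A Reported Medication Day is "a Reported eDiary Day where at least one of the following pieces of information are available". The three items are an answer in the headache diary ("Did you take any medications to treat this headache today"), in the evening diary ("Did you take any medication to prevent a headache today"), or to the medication question in the diary for aura without headache.
- **Numerator.** "A day where the participant answers that they took any of those in the diary is considered a day with use" of acute medication. A blank cannot count as use.
- **Missing days.** "A missing Medication Day is defined as a day that is not a Reported Medication Day". No rule covers a blank treatment question when another medication question was answered.
- **Prorating.** SAP 15.1.1 describes it as "imputing days with missing information with the observed mean number of migraine days in the period", and it applies from 14 reported days in 28. Only missing days are filled in.
- **Precondition.** Under SAP 3.7 a day of a reported headache is a Reported eDiary Day once "the participant has recorded the daily symptoms for at least one of the days spanned by this headache". Other days of that headache need no entry of their own.

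**The concern.** The evening question asks about prevention. A 'No' there says nothing about whether a headache was treated, yet it is enough to make the day fully reported for medication. With the treatment question blank, the missing answer is read as no use, on a day when use is more plausible than on a headache-free day.

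The SAP foresees headache days with incomplete entries. SAP 15.1.7 fills a missing pain score on a reported headache day from the other days of the same headache, and SAP 15.14.1 does not read missing symptoms as absent. SAP 15.14.2 extends a participant's last headache, if left open, to the last evening entry; that span can contain evening answers without treatment answers. Only the medication count turns the blank into a zero.

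At stake are two alpha-controlled tests (SAP 11.2, Steps 8 and 9) and the counts by drug class. The placebo-based multiple imputation in SAP 11.3.4.1 and 11.4.4 would not show the problem, because it acts only on data still missing after prorating.

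**Working it through.** The plan states no figure for this point, so there is none to reproduce. The check traces one day through the rules and then applies the SAP's own formula.

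**1. One day.** Take a Reported eDiary Day with a headache, the treatment question blank, the evening answer 'No', no aura-related intake and no dated intake covering the day.

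| Rule | Result |
|---|---|
| Denominator (SAP 15.1.5) | +1, because the evening answer exists |
| Numerator (SAP 15.1.5) | +0, because no positive answer exists |
| Missing Medication Day? | No, so not prorated |

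**2. Size of the undercount.** Assumptions, none given in the documents: 28 Reported eDiary Days; H = 20 headache days; use on headache days only, with probability u = 0.7; a share f of headache days affected, whether or not medication was used.

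- True count: H·u = 20 × 0.7 = 14.0
- As written: 28 × H·u·(1 − f) / 28 = 14.0 × (1 − f)
- Affected days treated as missing: 28 × H·u·(1 − f) / (28 − H·f)

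| f | True | As written | Treated as missing |
|---|---|---|---|
| 3% | 14.0 | 13.6 | 13.9 |
| 5% | 14.0 | 13.3 | 28 × 13.3 / 27 = 13.8 |
| 10% | 14.0 | 12.6 | 28 × 12.6 / 26 = 13.6 |

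With k affected days the undercount as written is u·k. Over u = 0.5 to 0.9 and k = 2 to 6 it runs from 0.5 × 2 = 1.0 to 0.9 × 6 = 5.4 days. Prorating recovers only part of it, because the blank days are all headache days while the mean that replaces them is taken over all reported days.

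**3. Treatment contrast.** In each arm the observed change is (1 − f_post) × post − (1 − f_base) × baseline. If f is the same in both arms and all periods, this is (1 − f) × the true change, so the between-group difference shrinks by the fraction f: a 2-day difference becomes 2 × 0.95 = 1.9 at f = 5%. If f varies by arm or period, the terms in f no longer reduce to a common factor, and the difference may be understated or overstated.

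**4. MOH status.** SAP 3.9.2 uses limits of 10 or 15 days. SAP 11.4.2 and 15.1.6 refer to data missing after prorating, so I assume that the class counts are prorated in the same way.

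- 9 observed days, 3 affected: 9.00 as written; 28 × 9 / 25 = 10.08 if treated as missing.
- 14 observed days, 2 affected: 14.00 as written; 28 × 14 / 26 = 15.08 if treated as missing.

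SAP 15.1.6 scores the composite as fulfilled if either CM or MOH is met. SAP 3.9.1 sets CM at 15 or more headache days with at least 8 migraine days. For anyone who meets CM, the medication count cannot alter Steps 5 and 6.

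**The case against.** SAP 3.6 requires participants to give medication intake on each day of a headache, and the evening diary sets off a routine that includes the headache diary. To produce the pattern, a participant must answer the evening question and leave the headache items blank. This stands as a reason to expect a low frequency. It does not rule the pattern out: neither document states that the treatment question is a forced item, and Protocol 9.2.1.2 leaves the details of the questions to a separate training module.

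Intake is also dated. Protocol 9.2.1.1 lists start and stop dates for acute medication, and SAP 15.1.5 uses such dates where intake crosses a 4-week boundary. A day's use may therefore be known without that day's own answer. This stands, and such days fall outside the point.

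The one-answer rule also has a purpose. On a day with neither headache nor aura the evening question is the only one that applies, so it must suffice there. The fix keeps that.

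Three stronger readings are tempting, and the documents do not support them:

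- **The rule always shrinks the treatment difference.** A reader might infer this from the undercount. It follows only if the affected share is equal across arms and periods, and the documents do not say so.
- **One blank day at the limit changes MOH status, and prorating restores it.** With 9 observed days and one blank, prorating gives 28 × 9 / 27 = 9.33, still below 10. Participants with many headache days will often meet CM already, so their composite result does not move.
- **Intake reported on a day that is not a Reported eDiary Day is lost.** Such a day is outside the denominator and is filled at the participant's observed mean when the period has enough reported days. The SAP does not say whether the intake stays in the numerator, which calls for clarification but shows no loss.

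**Conclusion.** The point holds in a limited form. The SAP's definitions, read together, give no use as the value for a headache day on which treatment is unknown, and the SAP's own missing-data rules show that such days are foreseen. On affected days where medication was taken, use is undercounted in the endpoints of Steps 8 and 9 and in the counts by drug class. Steps 5 and 6 are touched only through MOH status, for participants who do not meet CM and are near a limit, and only if class counts are prorated as assumed.

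At assumed shares of 3 to 10% the undercount is 0.4 to 1.4 days on a true 14.0 (14.0 − 13.6 and 14.0 − 12.6). The real share is unknown and may be small. No change in any test result is shown. The primary endpoint does not use this denominator.

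**What to change.** Reword the definition in SAP 15.1.5:

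- On a day with a headache, a Reported Medication Day needs a response to the treatment question for that headache. On a day with an aura without headache, it needs a response to the aura medication question.
- The exception is a day for which acute medication intake is already recorded in any part of the diary. That day counts as reported.
- On a day with neither event, the evening answer suffices.
- Any other day is a missing Medication Day and is prorated.
- Numerator and denominator use the same set of days.

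Tabulate the affected headache days by arm and 4-week period, so that their frequency is known. If the device already forces the treatment question, the SAP should say so.

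The cost is one paragraph and one derivation, with slightly more days prorated. Two imperfections remain. Prorating removes only part of the undercount. Keeping incomplete days with known intake while dropping incomplete days without it gives a small upward tendency.
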